### 10.3.7 Estimation of celecoxib excessive cardiovascular toxicity

We will use the design of Thall and Simon (1994) to continuously monitor grade 2 cardiovascular toxicities, with the trial suspended if the rate is deemed too high, the data reviewed, and only opened again after review by the NCI and IRB.

Let  $P$  represent the proportion of patients in the trial who experience at least one cardiovascular toxicity of grade 2 or higher during the 6 months on study drug. We will continuously monitor this quantity in the trial using the method of Thall and Simon (1994). We assume a diffuse prior distribution on  $P$ , specifically a Beta (0.02, 0.98), which has mean 0.02 and 95% credible interval (0,0.28). We will suspend accrual in the trial if, at any time during the trial,  $\Pr(P > 0.018) > 0.90$ . That is, we will stop the trial early if, based on the data in the trial, there is strong evidence (probability > 0.90) that the grade 2 cardiovascular toxicity rate is greater than 0.018. Based on this criterion, the trial will be terminated early for excessive toxicity if 2 or more of the first 10 patients enrolled on the trial experience a grade 2 or greater cardiovascular toxicity, or if 3 or more of the first 31 patients experience a grade 2 or greater cardiovascular toxicity, or if at any time during the study a 4th patient experiences a grade 2 or greater cardiovascular toxicity. With these stopping rules, the study will suspend accrual of new patients and celecoxib treatment of enrolled patient with probability 0.85 if, in fact,  $P=0.10$ , and with probability 0.46 if, in fact,  $P=0.05$ . If the true proportion is  $P=0.01$ , then the trial will stop with probability 0.04. (see reference 35).

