#### **9.8.0 Early stopping role for cardiovascular toxicity**

The proportion of subjects who developed serious cardiovascular adverse events while taking placebo was reported as 1.8 % in a large international study for the prevention of sporadic polyps, the Prevention of Spontaneous Adenomatous Polyps Trial. Based on this information, we have statistically estimated the numbers of cardiovascular events that will predict that celecoxib will have excessive cardiovascular toxicity (10.3.7). According to these calculations, we will suspend the study for excessive cardiovascular toxicity if 2 or more of the first 10 patients enrolled on the trial experience a grade 2 or greater cardiovascular toxicity, or if 3 or more of the first 31 patients experience a grade 2 or greater cardiovascular toxicity, or if at any time during the study a 4th patient experiences a grade 2 or greater cardiovascular toxicity. The study will be suspended by stopping enrollment of new subjects and celecoxib treatment for all enrolled patients. If the study is suspended, the IRB and NCI will be notified within 3 working days. The following study clinical investigators will review safety data: Drs. [name] and [name] in consultation with [name], study biostatistician and [name], collaborating cardiologist. A report of this safety review will be sent to MD Anderson IRB and the NCI. The study will be permanently stopped unless the MD Anderson IRB, NCI and study investigators all agree that the study can be safely resumed.

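### The cardiovascular stopping counts in 9.8.0 and 10.3.7 neither follow from the stated Bayesian criterion nor give the stated stopping probabilities; the written rule is much weaker than claimed

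*Combined protocol and SAP*

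**What the plan says.** Section 10.3.7 describes continuous monitoring of P, the proportion of patients with at least one cardiovascular toxicity of grade 2 or higher during the six months on drug. It gives three linked elements.

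- **Criterion.** With a Beta(0.02, 0.98) prior, the trial is suspended whenever "there is strong evidence (probability > 0.90) that the grade 2 cardiovascular toxicity rate is greater than 0.018". The 0.018 comes from section 9.8.0: "The proportion of subjects who developed serious cardiovascular adverse events while taking placebo was reported as 1.8" per cent in a large polyp-prevention trial.
- **Counts**, presented as the consequence of that criterion: "2 or more of the first 10 patients enrolled on the trial experience a grade 2 or greater cardiovascular toxicity", or 3 or more of the first 31, or a fourth affected patient at any point.
- **Stopping probabilities**, presented as those of the counts: "the study will suspend accrual of new patients and celecoxib treatment of enrolled patient with probability 0.85 if, in fact" P = 0.10; 0.46 at P = 0.05; and 0.04 at P = 0.01.

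Section 9.8.0, which tells staff when to act, repeats only the counts (for example "if 3 or more of the first 31 patients experience a grade 2 or greater cardiovascular toxicity") and refers to 10.3.7 for their basis. The planned sample size is 40 (sections 3.0 and 10.3.6).

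**The concern.** Each element is said to follow from the one before, so an error at either step leaves the trial with a safety boundary that is not the one described. Two things can be tested: whether the counts are those the posterior criterion implies, and whether the counts give the quoted probabilities over 40 patients.

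This is the only numerical trial-wide toxicity boundary in the plan. The dose is 400 mg twice daily, that is 800 mg a day, and section 9.4.0 itself cites a 3.4-fold rise in major cardiovascular events at that dose. Under 9.8.0 the IRB and NCI must agree before a suspended trial resumes, and they would rely on the quoted probabilities to judge how well the rule protects patients.

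**Working it through.** **Inputs.** Prior Beta(0.02, 0.98), threshold 0.018, cutoff 0.90, the three counts and the three stated probabilities, all from 10.3.7; N = 40 from 3.0 and 10.3.6.

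**Step 1: from criterion to counts.** After x events in n patients the posterior is Beta(0.02 + x, 0.98 + n − x). The criterion is met when its upper tail beyond 0.018 exceeds 0.90.

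| Events / patients | Pr(P > 0.018) | Criterion met? | Written counts suspend? |
|---|---|---|---|
| 1 / 6 | 0.902 | yes | no |
| 1 / 10 | 0.841 | no | no |
| 2 / 10 | 0.987 | yes | yes |
| 2 / 11 | 0.985 | yes | no |
| 2 / 20 | 0.952 | yes | no |
| 2 / 30 | 0.902 | yes | no |
| 2 / 31 | 0.896 | no | no |
| 3 / 31 | 0.983 | yes | yes |
| 3 / 32 | 0.981 | yes | no |
| 3 / 40 | 0.966 | yes | no |

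The criterion therefore stops the trial at 1 event within the first 6 patients, 2 within the first 30, or 3 up to patient 62, so a third event always qualifies among 40. It is met while the written counts let the trial continue at 1 event in patients 1–6, 2 events in patients 11–30 and 3 events in patients 32–40.

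A different cutoff does not explain the printed limits. For the two-event limit to be 10, the cutoff must lie between the values at 2/11 and 2/10 (0.985 to 0.987). For the three-event limit to be 31, it must lie between those at 3/32 and 3/31 (0.981 to 0.983). Both are far from 0.90, and they do not overlap.

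**Step 2: from counts to stopping probabilities.** Let X(n) be the number of affected patients among the first n, binomial with rate P. The written rule suspends if X(10) ≥ 2, X(31) ≥ 3 or X(40) ≥ 4. At P = 0.10:

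- by patient 10: 1 − 0.9^10 − 10 × 0.1 × 0.9^9 = 1 − 0.3487 − 0.3874 = 0.2639
- first crossing in patients 11–31: 0.3687
- first crossing in patients 32–40: 0.0518
- total: 0.2639 + 0.3687 + 0.0518 = 0.684, against the stated 0.85.

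The criterion's own boundary suspends if X(6) ≥ 1, X(30) ≥ 2 or X(40) ≥ 3. At P = 0.10 the chance of never crossing is 0.9^6 × [0.9^24 × Pr(B ≤ 2) + 24 × 0.1 × 0.9^23 × Pr(B ≤ 1)], where B is binomial(10, 0.1). This equals 0.5314 × [0.0798 × 0.9298 + 0.2127 × 0.7361] = 0.123, so the stopping probability is 0.877.

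The same calculations at the other rates give:

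| Rule, N = 40 | P = 0.10 | P = 0.05 | P = 0.01 |
|---|---|---|---|
| Stated in 10.3.7 | 0.85 | 0.46 | 0.04 |
| Written counts | 0.684 | 0.246 | 0.007 |
| Stated criterion | 0.877 | 0.540 | 0.082 |
| 2 in first 30, or 3 at any point | 0.857 | 0.478 | 0.037 |

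A simulation of 400,000 trials agrees with the last three rows. Checking the written counts only at patients 10 and 31, plus a fourth event whenever it occurs, gives the same values as checking after every patient.

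**Step 3: could a larger number treated explain it?** Section 7.12.0 replaces drop-outs without stating how many. The written counts give 0.790 / 0.309 / 0.008 at 50 patients and 0.878 / 0.397 / 0.009 at 60. Reaching the stated figures would take about 56, 66 and 118 patients respectively, so no single N fits all three.

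**The case against.** The strongest reply is that 10.3.7 also states the posterior criterion as a trigger in its own right. A statistician applying it directly would suspend with probability 0.877 at P = 0.10 and 0.540 at P = 0.05, more often than the plan claims. That is true, and it means the documents contain two conflicting triggers rather than one weak one. But the stated probabilities are attached to the counts, and 9.8.0 gives staff the counts alone. For a second event in patients 11–30, one section suspends the trial and the other does not.

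Other safeguards exist: individual discontinuation for possibly related grade 2 or higher cardiac toxicity and periodic cumulative review with a cardiologist (9.5.0), independent monitoring (9.5.1), and prompt IRB reporting of study-related events (9.7.1). A second event would be seen. These measures limit the practical harm, but none sets a numerical trial-wide boundary.

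With replacements, the gap at P = 0.10 could close: 0.790 at 50 patients and 0.878 at 60. This stands for that one figure; the gaps at 0.05 and 0.01 remain. At P = 0.01 the discrepancy means fewer false suspensions, so it is a mismatch and not a loss of safety.

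How the error arose is conjecture. The stated figures lie within 2 points of the rule in the last row of the second table, which is the criterion with a lone early event ignored. From patient 11 on, except at patient 31, that rule is one event stricter than the written counts. This suggests a slip in the printed counts. Lowering every count by one (1 in 10, 2 in 31, then 3) gives 0.895 / 0.589 / 0.113, which does not match. The finding does not depend on the explanation.

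**Conclusion.** The point holds and must be fixed. The counts do not follow from the criterion, and they do not have the stated stopping probabilities. If the counts are followed over 40 patients, the chance of suspension is 0.684 instead of 0.85 at a 10% rate (0.166 lower), 0.246 instead of 0.46 at 5% (0.214 lower, roughly half) and 0.007 instead of 0.04 at 1%.

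The posterior calculation uses only the stated prior, threshold and cutoff. The probabilities assume independent patients with a common rate and 40 patients treated; up to 60, the three stated figures are still not reproduced together. Calling the monitor weaker than stated assumes that the counts are what is applied, as 9.8.0 directs.

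**What to change.** Decide which element governs (the posterior criterion, the event counts, or the target stopping probabilities) and recompute the other two from it. Print the same counts and the exact stopping probabilities in 9.8.0 and 10.3.7. State the number of treated patients those probabilities assume, given that drop-outs are replaced, and say whether a single event among the first 6 patients is meant to suspend the trial. Which rule should govern is for the sponsor and its safety reviewers; this review does not choose.

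The cost is a recalculation and a wording amendment to two sections, with no added patients, visits or procedures.

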## 11.0 ETHICAL & REGULATORY CONSIDERATIONS

### 11.1 Institutional Review

This study must be approved by an appropriate institutional review committee as defined by Federal Regulatory Guidelines (Ref. Federal Register Vol. 46, No. 17, January 27, 1981, part 56). The protocol and informed consent form for this study must be approved in writing by the appropriate Institutional Review Board (IRB). The IRB must be from an institution which has a valid Multiple Project Assurance, Single Project Assurance or Cooperative Oncology Group Assurance on file with the Office for Protection from Research Risks, National Institutes of Health. The institution must be in compliance with regulations of the Food and Drug Administration and the Department of Health and Human Services.

Significant changes to the protocol, as well as a change of principal investigator, must also be approved by the Board and documentation of this approval provided to the study monitor. Records of the Institutional Review Board review and approval of all documents pertaining to this study must be kept on file by the investigator and are subject to FDA inspection at any time during the study. Periodic status reports must be submitted to the Institutional Review Board at least yearly, as well as notification of completion of the study and a final report within 3 months of study completion or termination. The investigator must maintain an accurate and complete record of all submissions made to the Institutional Review Board, including a list of all reports and documents submitted.

